10.1.4 Suspected unexpected serious adverse reactions (SUSARs)

A SUSAR is an SAE suspected to be related to a product, which is of a **type or severity** which is NOT consistent with the Summary of Product Characteristics (SPC) for oxytocin (see Section 10.2 for further details).

10.2 Expected Adverse Reactions (ARs)

Expected ARs are those listed in the current Summary of Product Characteristics (SPC) for oxytocin. These events do not meet the criteria of Suspected Unexpected Serious Adverse Reaction (SUSAR) unless for reason of their severity. For convenience, a summary of the expected ARs for oxytocin given in the SPC (as Syntocinon[®], Novartis) are listed in Appendix One and Two (see SPC sections 4.8 Undesirable effects) and comprise the Reference Safety Information (RSI).

10.2.1 Expected ARs for maternal outcomes

There are a number of expected ARs in mother listed in section 4.8 of the SPC (see Appendix 1 & 2), which are considered to be of 'common' frequency and for convenience are listed, but are not limited to, below:

- headache
- nausea
- vomiting
- tachycardia/bradycardia

ARs occurring in mother will be recorded on the Labour Form. Occurrence will be confirmed by the local obstetrician and midwife, recorded on the CRF and returned to the Trial Office. They will be reported to the DMC when it meets.

10.2.2 Expected ARs for labour outcomes

There are a number of expected ARs for labour outcomes listed in section 4.8 of the SPC (see Appendix 1 & 2), which are considered to be of 'not know' frequency (i.e., isolated reports that cannot be estimated from the available data) and for convenience are listed, but are not limited to, below:

- uterine tachysytole (defined as more than 5 contractions in 10 minutes for 20 minutes)
- uterine hyperstimulation (defined as tachysystole with non-reassuring or abnormal features of the fetal heart rate)

Our pilot study found that 17% of the standard dose group (8/47) had an episode of uterine tachysystole with 11% (5/47) experiencing hyperstimulation. With our proposed sample of 1,500 women, we would have 80% power to detect an absolute increase of 6% in the rate of tachysystole (i.e. 17% to 23%) and a 5% increase (i.e. 11% to 16%) for hyperstimulation.

ARs occurring in labour will be recorded on the Labour Form. Occurrence will be confirmed by the local obstetrician and midwife, recorded on the CRF and returned to the Trial Office. They will be reported to the DMC when it meets.

10.3 Expected SARs

In addition to the definition of a SAR given in section 10.1.3, the following (listed for convenience, but are not limited) have a causal association with the trial drug and should be reported as a SAR:

- maternal anaphylaxis
- maternal pulmonary oedema

For details on how to report SARs please see Section 10.5 – Reporting of SARs/SAEs.

10.4 Expected SAEs

In addition to the definition of a SAE given in section 10.1.3, the following events (listed for convenience, but are not limited) do not have a causal association with the trial drug and should be reported as a SAE:

Maternal outcomes

• uterine rupture/ hysterectomy

- postpartum haemorrhage that triggers the Massive Obstetric Haemorrhage protocol, including blood transfusion
- maternal admission to HDU/ITU- requiring critical care level 2 or 3 as defined by national criteria categorised by us
- maternal death

Neonatal outcomes

- unexpected provision of neonatal intensive care
- neonatal seizures
- neonatal encephalopathy
- the need for neonatal therapeutic hypothermia and
- Intrapartum stillbirth
- neonatal death

For details on how to report SAEs please see Section 10.5 – Reporting of SARs/SAEs.

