10.5 Reporting SARs/SAEs

All maternal or neonatal SARs/SAEs, from the commencement of the trial treatment until discharge from hospital, must be recorded on the SAE form and faxed to BCTU on [name] within 24 hours of the research staff becoming aware of the event. Alternatively, the report can be emailed as a PDF attachment to the HOLDS email address from a NHS email account. The Principal Investigator (or other nominated obstetrician) is required to assign seriousness, causality and expectedness to the SARs/SAEs before reporting. All SARs/SAEs should be assessed for seriousness, causality and expectedness.

For each SARs/SAEs, the following information will be collected:

- full details in medical terms with a diagnosis, if possible
- its duration (start and end dates; times, if applicable)
- action taken
- outcome
- causality, in the opinion of the investigator*
- whether the event would be considered expected or unexpected* (refer to Reference Safety Information)

*Assessment of causality and expectedness must be made by an obstetrician. If an obstetrician is unavailable, initial reports without causality and expectedness assessment should be submitted to Trial Office by a healthcare professional (i.e., HOLDS midwife) within 24 hours, but must be followed up by medical assessment as soon as possible thereafter, ideally within the following 24 hours.

The local Principle Investigator and others responsible for the woman's or baby's care should institute any supplementary investigations of SARs/SAEs based on their clinical judgement of the likely causative factors and provide further follow-up information as soon as available.

SARs/SAEs still present beyond 28 days post-partum must be followed up until the final outcome is determined.

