10.6 Reporting SUSARs

SAEs categorised by the local investigator as **both** suspected to be related to the trial drug **and** unexpected are SUSARs, and are subject to expedited reporting. All SUSARs must be recorded on the SAE Form and faxed to the BCTU on [name]. Alternatively, the report can be emailed as a PDF attachment to the HOLDS email address from a NHS email account, within 24 hours of the research staff becoming aware of the event. The Chief Investigator (CI) or nominated individual will undertake urgent review of SUSARs within 24 hours of reporting and may request further information immediately from the patient's clinical team. The CI will not overrule the causality, expectedness or seriousness assessment given by the local investigator. If the CI disagrees with the local investigator's assessment, further clarification and discussion should take place to reach a consensus. If a consensus cannot be reached, both the opinion of the local investigator and the CI should be provided in the report to the MHRA and the REC.

The BCTU will report all SUSARs to the MHRA and the main REC. If the SUSAR resulted in death or was life-threatening this will be done within 7 days of the initial report being received or within 15 days for any other SUSAR. If information is incomplete at the time of initial reporting, or the event is ongoing, the BCTU will request follow-up information, including information for categorisation of causality, from the local investigator and will send the follow-up information to the MHRA and main REC within an additional 8 days for fatal or life-threatening SUSARs and as soon as possible for any other events.

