The adverse drug reactions derived from post-marketing experience with Syntocinon are via spontaneous case reports and literature cases. Because these reactions are reported voluntarily from a population of uncertain size, it is not possible to reliably estimate their frequency which is therefore categorised as not known. Adverse drug reactions are listed according to system organ classes in MedDRA. Within each system organ class, ADRs are presented in order of decreasing seriousness.

System organ class	Adverse drug reaction
Immune system disorders	Rare: Anaphylactic/ Anaphylactoid reaction associated with dyspnoea, hypotension or Shock
Nervous system disorders	Common: Headache
Cardiac disorders	Common Tachycardia, bradycardia Uncommon: Arrhythmia Not known: Myocardial ischaemia, Electrocardiogram QTc prolongation
Vascular disorders	Not known: Hypotension, haemorrhage
Gastrointestinal disorders	Common: Nausea, vomiting
Skin and subcutaneous tissue disorders	Rare: Rash
Pregnancy, puerperium and perinatal conditions Metabolism and nutrition disorders	Not known: Uterine hypertonus, tetanic contractions of the uterus, rupture of the uterus Not known: Water intoxication, maternal hyponatraemia

Respiratory, thoracic and mediastinal disorders	Not known: acute pulmonary oedema
General disorders and administration site conditions	Not known: Flushing
Blood and lymphatic system disorders Skin and subcutaneous tissue disorder	Not known: disseminated intravascular coagulation Not known: Angioedema

Table 2 Adverse drug reactions in foetus/neonate

System organ class	Adverse drug reaction
Pregnancy, puerperium and perinatal conditions	Not known: foetal distress, asphyxia and death
Metabolism and nutrition disorders	Not known: Neonatal hyponatraemia

Reporting of suspected adverse reactions

Reporting of suspected adverse reactions after authorisation of a medicinal product is important. It allows continued monitoring of the benefit/risk balance of a medicinal product. Healthcare professions are asked to report any adverse reactions via Yellow Card Scheme (www.mhra.gov.uk/yellowcard)

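### Section 10.4 labels as expected some SAEs that the Reference Safety Information does not list, so a related case could be kept out of expedited reporting

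*Combined protocol and SAP*

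**What the plan says.** Three sections tie expectedness to the SPC. Section 10.1.4 defines a SUSAR as a suspected related event whose type or severity does not fit the SPC. Section 10.2 states "Expected ARs are those listed in the current Summary of Product Characteristics (SPC) for oxytocin" and names the section 4.8 listings in Appendices One and Two as the RSI. Section 10.5 makes one of the data items for every SAR or SAE "whether the event would be considered expected or unexpected* (refer to Reference Safety Information").

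Section 10.4, headed "10.4 Expected SAEs", lists ten maternal and neonatal items, among them "maternal death", "uterine rupture/ hysterectomy", neonatal seizures and neonatal encephalopathy. Its introductory sentence says that the listed events "do not have a causal association with the trial drug and should be reported as a SAE". It then sends the reader to 10.5 for the reporting procedure.

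Under 10.6, events that the local investigator calls both related and "unexpected are SUSARs, and are subject to expedited reporting". The limit is 7 days if the event was fatal or life-threatening and 15 days otherwise. Under 10.5, SARs and SAEs in general go to the MHRA and REC annually.

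**The concern.** The word *expected* decides a regulatory route in this protocol, and 10.4 applies it to events that the RSI does not contain. The two preceding headings use it in the RSI sense. Section 10.2 cites the SPC directly, and both examples in 10.3 (anaphylaxis and pulmonary oedema) are in the SPC tables. Nothing in 10.4 says that the meaning changes.

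Two obstetricians assessing the same related case could therefore complete the expectedness item differently, depending on whether they look at 10.4 or at the RSI. Maternal death and neonatal encephalopathy are among the gravest events the trial could see, in a comparison where one arm receives double the concentration. Late notice to the regulator and the ethics committee matters most for events like these.

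**Working it through.** No arithmetic applies. The check sets each item of 10.4 against the text and tables of SPC section 4.8, which agree in Appendices One and Two on these items.

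| Item in 10.4 | SPC section 4.8 |
|---|---|
| Uterine rupture / hysterectomy | Rupture listed; hysterectomy not listed |
| Massive postpartum haemorrhage | Haemorrhage listed |
| Maternal HDU/ITU admission | Not listed (a level of care) |
| Maternal death | Not listed; the death in 4.8 is foetal or neonatal |
| Neonatal intensive care | Not listed (a level of care) |
| Neonatal seizures | Not in the foetus/neonate table; grand-mal type seizures appear in the narrative as a symptom of water intoxication |
| Neonatal encephalopathy | Not listed; asphyxia is |
| Therapeutic hypothermia | Not listed (a procedure) |
| Intrapartum stillbirth | Covered by death in the foetus/neonate table |
| Neonatal death | Covered by death in the foetus/neonate table |

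The foetus/neonate table has two entries: "Not known: foetal distress, asphyxia and death", and neonatal hyponatraemia.

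The items are not equally strong as examples:

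- **Maternal death and neonatal encephalopathy** are the clearest. Both are clinical events, and neither is in 4.8.
- **Neonatal seizures** are weaker. Section 4.8 associates water intoxication with maternal and neonatal hyponatraemia and names seizures among its symptoms. The accurate statement is that they are not listed as a neonatal reaction.
- **Hysterectomy, hypothermia and the two care levels** add little. Section 10.1.2 says that diagnostic and therapeutic procedures are not AEs, and expectedness would turn on the underlying event, which may itself be in the RSI.

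Now follow a case of neonatal encephalopathy that the investigator judges related:

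1. Assessed against the RSI, as 10.5 directs, it is not listed and so is unexpected. It is related and unexpected, hence a SUSAR, and goes to the MHRA and REC within 7 or 15 days.
2. Assessed from the 10.4 heading, it is expected. It fails the second condition of 10.6 and reaches the MHRA and REC in the annual report.

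The introductory sentence of 10.4 bears on the first condition in the same way. It declares the listed events unrelated in advance, whereas 10.5 asks for a causality judgement on each case. It also conflicts with the RSI, which lists rupture of the uterus and foetal or neonatal death as adverse drug reactions. The heading conflict is separate and would remain if that sentence were deleted.

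**The case against.** The best defence is that the protocol has one operative rule for expectedness, and 10.4 is not part of it. The word appears there only in a heading. The body of 10.4 tells sites to report the events and points to 10.5, which names the RSI as the standard and requires assessment case by case. The list even contains an item described as unexpected (neonatal intensive care), which suggests that the heading means anticipated in this population. For a maternal death, 10.1.4 and 10.2 already allow severity beyond the SPC to make an event a SUSAR.

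There are also safeguards. SAEs reach the trials unit within 24 hours of staff becoming aware. The CI assesses causality and expectedness, with confirmation by an obstetric or neonatal co-applicant, and can alert the DMC chair (10.5, 10.7.2). Fatal SAEs go to the DMC for continuous review (10.7.3), and the DMC sees unblinded safety data, initially about every six months (10.5, 10.7.5). The statement in 10.6 that the CI will not overrule the local assessment concerns the review of events already called SUSARs. It does not clearly prevent a central query about an event called expected.

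Most of this stands, and it limits the point to a risk. It does not remove the conflict. The severity provision shows what the RSI rule would conclude, which is the opposite of the 10.4 label. Central reviewers work from the same protocol and meet the same heading. DMC review protects participants but is not the expedited report to the MHRA and REC.

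**Conclusion.** The point holds as an inconsistency between a heading and the protocol's own standard for expectedness. An assessor who relies on the heading could take a related maternal death or neonatal encephalopathy off the 7- or 15-day route and leave it for the annual report. That outcome requires three things: the event is judged related, the assessor follows 10.4 and not 10.5, and central review does not correct the entry.

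A reader might infer more than the documents support:

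- **That related cases will miss SUSAR status.** Section 10.5 points to the RSI, so the documents show only that they could.
- **That most of the 10.4 list is misclassified.** Several items are procedures or levels of care, and seizures are mentioned in 4.8.
- **That an assumed incidence applied to 1500 women gives the number of cases at stake.** The documents give no incidence, and only cases judged related could change route. No number can be given.
- **That the regulatory delay leaves the trial without oversight in the meantime.** The trials unit, CI and DMC routes continue to operate.

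**What to change.** In the next amendment:

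1. Retitle 10.4 *SAEs anticipated in this population (to be reported)*.
2. Add: *Listing here does not make an event expected; expectedness for SUSAR purposes is assessed only against SPC section 4.8 (the RSI).*
3. Reconcile the introductory sentence of 10.4 on causality with the case-by-case assessment in 10.5 and with the RSI.

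No change to the SAE form is proposed: the form is not in the documents, and 10.5 already refers its expectedness item to the RSI. The cost is a new heading, an added sentence and a reworded one, with possibly a few more expedited reports. Treatment, data collection and analysis are unaffected.

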10.7 Safety reporting responsibilities

10.7.1 Local Principal Investigator (or nominated individual in PI's absence)

- To record all safety events that occur in the women taking part in the trial. This includes serious, expected or unexpected adverse events, unless defined as outcomes above
- Medical judgement in assigning expectedness and causality to SAEs
- To fax SAE forms to BCTU within 24 hours of becoming aware, and to provide further followup information as soon as available
- To report SARs/SAEs to local committees if required, in line with local arrangements
- To sign an Investigator's Agreement accepting these responsibilities

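### Section 10.4 declares ten serious event types unrelated to oxytocin, against the trial's own Reference Safety Information and the case-by-case causality assessment in Section 10.5

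*Combined protocol and SAP*

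**What the plan says.** Section 10.4 (Expected SAEs) introduces its list with the statement that the events "do not have a causal association with the trial drug and should be reported as a SAE". The maternal items are "uterine rupture/ hysterectomy", "postpartum haemorrhage that triggers the Massive Obstetric Haemorrhage protocol, including blood transfusion", critical-care admission and maternal death. The neonatal items are unexpected intensive care, seizures, encephalopathy, therapeutic hypothermia, "Intrapartum stillbirth" and neonatal death. The section then sends the reader to 10.5 for reporting.

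Section 10.2 designates SPC section 4.8, reproduced in Appendices One and Two, as the RSI. Its maternal reaction table includes "Not known: Uterine hypertonus, tetanic contractions of the uterus, rupture of the uterus" and a generic haemorrhage entry under vascular disorders. Its foetus/neonate table includes "Not known: foetal distress, asphyxia and death".

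Section 10.3 is the mirror image of 10.4. It names maternal anaphylaxis and pulmonary oedema as causally linked to the drug and to be reported as SARs. Section 10.5 requires seriousness, causality and expectedness to be assessed for every SAR and SAE, with causality and expectedness judged by an obstetrician.

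Section 10.7.1 describes the Principal Investigator's duty to record safety events and adds: "This includes serious, expected or unexpected adverse events, unless defined as outcomes above".

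**The concern.** Sections 10.3 and 10.4 together sort serious events into causal and non-causal before any case has been seen. Section 10.5 then asks for a judgement on each case. A site therefore has two instructions that cannot both be followed for the ten events in 10.4, and one of them disagrees with the document against which expectedness is to be judged.

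This matters because the safety of the high dose is a stated secondary objective (6.3) and the high-dose solution has double the concentration (8.1). SPC 4.8 itself links overstimulation at too high doses to uterine rupture and to foetal distress, asphyxia and death. An investigator who takes 10.4 at face value may code as unrelated some of the harms for which an unbiased opinion is most needed. Whether an event is a SAR or a SUSAR depends on that opinion.

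**Working it through.** The point rests on text, so the check sets the passages side by side.

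**1. The 10.4 list against the RSI.** The list has 4 + 6 = 10 event types. The two SPCs agree on these entries.

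| Event in 10.4 | RSI tables (SPC 4.8) | Too-high-dose sentence in SPC 4.8 |
|---|---|---|
| Uterine rupture/hysterectomy | Rupture named; hysterectomy not | Rupture named |
| Massive postpartum haemorrhage | Haemorrhage, generic | Not named |
| Intrapartum stillbirth | Falls under death, foetus/neonate table | Falls under death |
| Neonatal death | Falls under death, foetus/neonate table | Not separately named |
| Maternal critical-care admission, maternal death, neonatal intensive care, seizures, encephalopathy, therapeutic hypothermia | Not named | Not named |

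So 4 of 10 items have an RSI counterpart, one of them by name, and 6 of 10 do not. The blanket statement in 10.4 covers all ten.

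**2. 10.4 against 10.5.** Section 10.5 records causality as the investigator's opinion on each event. If 10.4 were true, that field would have only one permitted answer for the ten events.

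**3. Consequence for classification.** Under 10.1.4 and 10.6 a SUSAR must be suspected to be related and also unexpected.
- Events in the RSI: if judged related they are normally expected SARs, because 10.2 excludes them from SUSAR status unless their severity is the reason. A wrong unrelated call removes a SAR from the count but would rarely remove an expedited report.
- Events not named in the RSI tables: if judged related they could be SUSARs, due within 7 days if fatal or life-threatening and 15 days otherwise (10.6). Section 10.4 calls them expected in its title and non-causal in its text, so it answers both parts of the test in advance.

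The second group is not clear-cut. The SPC 4.8 narrative mentions seizures as a symptom of water intoxication, and a reader could treat encephalopathy as a form of the listed asphyxia. That is a reason to judge expectedness from SPC 4.8 and not from the title of 10.4.

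**4. Who decides.** Section 10.6 makes SUSAR status follow the local investigator's categorisation and bars the Chief Investigator from overruling it. Unresolved disagreement is sent to the MHRA and REC as two opinions.

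**5. Can the comparison by arm stand in for causality coding?** With n = 1,500/2 = 750 per arm and two-sided 5% (assumed, since 10.2.2 gives no alpha):

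power = Φ[(|p1 − p2| − 1.96·√(2p̄(1 − p̄)/n)) / √((p1(1 − p1) + p2(1 − p2))/n)]

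The protocol's own safety figures in 10.2.2 reproduce: 17% against 23% gives 82.8% and 11% against 16% gives 80.9%, in line with the stated 80%. Those cover only tachysystole and hyperstimulation. The documents give no rates for the 10.4 events, so the control rates below are assumptions. At 0.5% doubled to 1%: (0.005 − 1.96 × 0.004455)/0.004454 = −0.838, and Φ = 20%.

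| Assumed control rate | Doubled to | Expected events per arm | Power |
|---|---|---|---|
| 0.1% | 0.2% | 0.75 v 1.5 | 7% |
| 0.5% | 1% | 3.75 v 7.5 | 20% |
| 1% | 2% | 7.5 v 15 | 36% |

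The normal approximation is rough at such counts. It is enough to show that, for events this rare, a comparison by arm would be weak and individual causality assessment would carry real weight.

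**The case against.** The strongest defence is that 10.4 is loose drafting which the rest of Section 10 corrects. It points to 10.5, which demands an individual causality opinion. Sections 10.5 and 10.7.2 add review by the Chief Investigator, agreed with an obstetric or neonatal co-applicant. The DMC receives every SAR and SAE unblinded (10.5), and fatal events go to it for continuous review (10.7.3). Most of the events are also secondary outcomes, to be summarised or compared by arm, and counts by arm do not depend on a causality label.

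Most of this stands, and it rules out several stronger readings:
- A reader might infer that no uterine rupture or stillbirth could ever become a SAR or SUSAR. That follows only if 10.4 is read without 10.5.
- A reader might infer that the DMC would miss these harms. It would not, because it sees the events whatever their label.
- A reader might infer that expedited reporting fails for uterine rupture. As an RSI event it would normally be an expected SAR in any case.
- A reader might infer that the SPC ties haemorrhage to too high doses. The relevant sentence does not mention it.
- A reader might infer that 10.7.1 excuses sites from recording these events. Sections 10.4 and 10.5 specifically require them to be reported, so the exemption is a secondary conflict.

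What the defence does not remove is the contradiction. The Chief Investigator and co-applicants work from the same 10.4 text, and neither the DMC listing nor the outcome tables correct a causality code.

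**Conclusion.** The concern holds as a contradiction between current sections. Section 10.4 states a causality answer for ten serious event types. Four of these have a counterpart in the RSI, and 10.5 reserves the answer for individual assessment in all ten. The likely damage is to causality coding and SAR classification. For the events not named in the RSI tables it may extend to expedited reporting, on the assumption that they would be judged unexpected against SPC 4.8. The documents do not support a claim that events would go uncounted or be hidden from the DMC. How many events would be miscoded cannot be estimated, because it depends on how many investigators follow 10.4 over 10.5 and on event rates that the documents do not give.

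**What to change.** - **10.4:** delete the clause denying a causal association, so that the sentence only tells sites to report the listed events as SAEs. Add that causality is assessed case by case under 10.5 and that expectedness is judged only against SPC 4.8, not from the section title.
- **10.3:** do not move the events there. Its text asserts a causal link for everything it lists, which would replace one blanket judgement with its opposite.
- **10.7.1:** reconcile the outcome exemption with 10.4 and 10.5 so that it cannot apply to serious events. It should also say which outcomes it means, since Section 9 lists most of these events as outcomes and 10.4 itself uses outcome subheadings.

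The cost is a wording amendment, a note to sites and slightly more causality assessment work. No new data are needed.
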